5.2 Definition of Definitive Device

Definitive device is defined as a closed loop feedback (servo regulated) surface cooling device that can be used 1) to induce body temperature to a target of 33°C, 2) to maintain therapeutic hypothermia within a range of 32 to 34°C, and 3) to slowly rewarm or maintain at a normal temperature range (36-37.5°C). The device must be a FDA cleared device.

5.3 Temporary or Permanent Early Cessation of Cooling

In certain instances, it may be necessary to disconnect the participant from the definitive cooling device such as during participant transport to and from diagnostic or therapeutic procedures. Interruptions in active

temperature management should be minimized but brief periods of less than 30 minutes are allowed if monitored with central temperature monitoring. For longer periods of potential interruption, the definitive cooling device should accompany the participant and be re-instituted as soon as possible, during the procedure to avoid temperature excursions. MRI would be an exception. Core temperatures should be monitored continuously and documented at least every 30 minutes during interruptions in cooling. The clinical team along with parents or legally authorized representatives may alter the depth and duration of cooling, although this is discouraged without a clinical reason.

5.4 Clinical Standardization

A clinical standardization guideline will be followed to reduce the effects of practice variability subsequent to randomization. Key physiologic and practice variables will be tracked and compliance with clinical standardization and deviation from physiologic targets reported back to study teams. Clinical standardization guidelines will include but may not be limited to the following: avoiding hypotension, avoiding hypoxia, treatment of seizures, management of sedation and paralysis, and defining and treating infections. Additional parts of clinical standardization may include monitoring of chemistries, CBC, coagulation tests and blood gases. Clinical standardization guidelines state that neurologic prognostication leading to withdrawal of life support is only allowed after 120 hours. The exception is when a participant meets the full brain death criteria at the clinical site. Recently, guidelines for post resuscitation management have been published by an expert international multidisciplinary group (Topjian, 2019, e194).

6. OUTCOMES

6.1 Primary Efficacy Outcome

Primary Efficacy Outcome. The primary outcome will be the “VABS-3 Mortality Composite Score” in which enrolled participants who die before the 12-month outcome are scored 0 and the age-adjusted standardized VABS-3 composite score is assigned for the survivors (Sparrow , 2016). Measured VABS-3 composite scores range from 20-140 (mean=100, SD=15). The VABS-3 Mortality Composite Scores will be compared across treatment groups at 12 months after OHCA. The VABS-3 measures three core domains of neurobehavioral function (communication, daily living, socialization). These 3 core domains yield age-corrected standardized scores that contribute equally to an overall adaptive behavior composite score. The VABS-3 is applicable from birth through adulthood and has strong reliability and validity in children of all ages. Of note, no NIH toolbox neurobehavioral outcome measures are validated for children under age 3, and the measures for pre-school children function poorly for those with significant impairments.

The previous version of the Vineland (VABS-II) (Sparrow, 2005) was used as the primary outcome for the THAPCA trials and is no longer available. The new VABS-3 has updated content to reflect changes in everyday

life (e.g., new technology) and provides an online administration format using a computer or tablet that guides the examiner in the structured interview process by tracking item content and applying basal and ceiling rules.

In survivors, VABS-3 data will be obtained, using this format for structured telephone interviews, scheduled at 3 and 12 months after OHCA. Data will be collected by a trained interviewer, unaware of treatment allocation, at a central outcome center (KKI) with extensive experience and familiarity with this tool and method of data collection. Each interview is expected to take 30 to 45 minutes. The VABS-3 item content is available in English and Spanish. Spanish speaking interviewers will interview Spanish speaking caregivers.

Analysis of THAPCA-OH VABS-II scores revealed very strong correlations ($r=0.95$) of 3 and 12-month composite scores, even in infants ($r=0.88$); these findings support use of the 3-month VABS-3 scores to inform adaptive allocation until the 12-month outcome scores are available (Slomine, 2019). We anticipate that most enrolled OHCA cases will be under age 2 years; in such young children, sole reliance on performance at 3 months after OHCA as the primary outcome would be difficult to justify to many stakeholders (clinicians and families). Inclusion of a 12-month recovery period will likely strengthen the generalizability and acceptance of the P-ICECAP findings.

In THAPCA-OH, pre-OHCA functioning was evaluated within 24 h of enrollment using VABS-2; >90% had broadly normal function. Based on these data, coupled with feedback from the Collaborative Pediatric Critical Care Research Network (CPCCRN) – Family Network Collaborative that a lengthy structured interview within the first day after OHCA would be viewed unfavorably, no baseline VABS-3 score will be obtained. Pediatric Cerebral Performance Category data (see below) will be used to verify that baseline pre-OHCA function does not differ among treatment groups (Fiser, 1992).

6.2 Safety Outcomes

The primary safety outcome is all-cause mortality at 30 days. All-cause mortality is selected because it incorporates the most severe irreversible safety consequences across many potential adverse events. Safety problems that are not reflected in either neurological recovery (the efficacy outcome measure) or mortality (the primary safety measure) do not generally cause any permanent morbidity and are therefore secondary. In THAPCA-OH 28-day mortality was used and trended lower in the hypothermia group than normothermia group (57% vs. 67%; $p=0.08$) (Moler, 2015). In THAPCA-OH the most common cause of death was brain death or severe neurologic injury occurring in approximately 80% of both groups.

6.3 Secondary and Exploratory Efficacy Measures

Secondary Measures – Global Functioning. The Pediatric Cerebral Performance Category (PCPC) and Pediatric Overall Performance Category (POPC) (Fiser, 1992) are 6-point categorical rating scales that include death in the scaling (range normal =1 to death =6). The PCPC rates neurological functioning, whereas the POPC rates

overall health. These scales were included in the 1995 Pediatric Utstein template of recommended guidelines for reporting outcomes of pediatric advanced life support (Perkins , 2015) and have been used extensively to measure CA outcomes (Moler , 2009; Moler , 2015; Sparrow , 2005; Topjian , 2008; Andersen , 2015; Matos , 2013). Most recently, the PCPC was recommended as part of the core outcome set for pediatric cardiac arrest research (Topjian , 2020). The PCPC and POPC will be collected based on review of medical record and caregiver interview within 24 hours of admission for baseline score, and at hospital discharge or at day 30, whichever is first (Topjian , 2020). Age-appropriate PCPC/POPC rating instructions, developed for the THAPCA trials, will be provided to ensure consistent ratings across sites. PCPC/POPC will also be scored at 3 and 12 months by the P-ICECAP neuropsychologist (BS) based on the VABS-3 interview responses. The change in PCPC score from 12 months minus baseline (delta PCPC) will be evaluated.

Neurological Functioning. At 12 months, survivors will undergo a neurological evaluation at their local site. Neurologists will describe the findings of a detailed age-appropriate neurological exam and provide global scores (from 0, normal, to 3, severe impairment) in 7 domains (total score range: 0-21), using the Pediatric Resuscitation after Cardiac Arrest (PRCA) measure, which was adapted from the Pediatric Stroke Outcome measure. PRCA scores obtained in THAPCA were strongly correlated with the VABS-II scores; 16/75 OHCA survivors had normal neurological exams (score “0”) (Ichord , 2018). Motor function in P-ICECAP will primarily be assessed by this measure. Deaths will be assigned the worst score, 21.

Survival at 12 months. Survival status is a standard outcome reported in cardiac arrest trials (Topjian , 2020).

Quality of Life (QL) and Family Burden (exploratory). In survivors, the PedsQL caregiver-report measures will be collected at 3 and 12 months to measure quality of life and family burden. To measure quality of life, caregivers of participants 2-18 years will complete the physical, emotional, social and school functioning scales of the PedsQL generic core measure (53) and supplemental cognitive function and daily living scales (Varni , 2002; Varni , 2006). Caregivers of participants who are still <2 years at 3 and 12 month time point will complete the infant version (Varni , 2011) which consists of 5 scales (adding Physical Symptoms and replacing “School” with Cognitive Functioning). Reliability and validity are adequate across numerous health conditions (Uzark , 2008; McCarthy , 2005). Family burden will be measured using the family impact module of the PedsQL which includes caregiver self-ratings of physical, emotional, social, and cognitive functioning, communication, and worry as well as the impact of their child’s health condition on daily activities and family relationships (Varni , 2004).

From THAPCA-OH we reported findings for each of the above outcomes (Moler , 2015 Slomine , 2019; Ichord , 2018; Slomine , 2016; Silverstein , 2016; Meert , 2016) and results included follow up in 98% of survivors at 12 months for the primary outcome measure. Methods used to achieve this high rate have been reported (Gildea 2020).

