4.2 Exclusion Criteria and Rationale

Criteria

Exclusion Criteria

- Glasgow Coma Motor Score (GCMS) = 6
- LAR does not speak English or Spanish
- Duration of CPR > 60 minutes
- Severe hemodynamic instability requiring continuous infusion of epinephrine or norepinephrine of 2 µg/kg/minute or initiation of ECMO
- Pre-existing severe neurodevelopmental deficits with PCPC =5 or progressive degenerative encephalopathy
- Pre-existing terminal illness, unlikely to survive to one year
- Cardiac arrest associated with brain, thoracic, or abdominal trauma
- Active and refractory severe bleeding prior to randomization
- Extensive burns or skin lesions incompatible with surface cooling
- Planned early withdrawal of life support before 120 hours
- Sickle cell anemia
- Pre-existing cryoglobulinemia
- Non-fatal drowning in ice covered water
- Central nervous system tumor with ongoing chemotherapy
- Previous enrollment in P-ICECAP trial
- Prisoner
- Chronic hypothermia
- New post-cardiac arrest diabetes insipidus
- Pregnancy

Rationale for selected eligibility criteria - Exclusions:

Participants with GCMS of 6 lack evidence of brain injury and are outside the scope of this trial.

Legally authorized representative (LAR) does not speak English or Spanish is excluded because the VABS-3 is not available in other languages.

Participants with OHCA CPR duration of >60 minutes are expected to have profound brain injury and may not benefit from hypothermia.

Severe hemodynamic insufficiency requiring high vasoactive doses or ECMO and/or ECMO during CPR to achieve return of circulation for OHCA is associated with very high mortality and is not offered at many hospitals.

Several pre-existing conditions may confound the outcome determination. Examples include participants with severe baseline neurodevelopmental deficits (PCPC =5) would likely not have measurable changes in VABS-3 except for death.

A progressive, degenerative encephalopathy may lead to worsening by the time the primary outcome is assessed independent of the intervention.

Patients with preexisting terminal conditions would not be able to contribute outcome data if they are not expected to survive to the one year neurological outcome assessment.

Severe trauma raises concern for exacerbating hemorrhage. Cooling for treatment of severe head trauma has been studied previously and had no benefit on patient outcome.

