9.1 Primary Endpoint

The VABS-3 ranges from 20 to 140 (mean age-corrected standardized score of 100) where higher scores indicate better cognitive outcomes. Deaths are assigned a score of 0. The VABS-3 Mortality Composite Score will analyze the combined deaths and survivors in a single analysis.

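### Delta PCPC (12 months minus baseline) can score a death as a smaller loss than survival at PCPC 5 when the two children had different baselines

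*Protocol*

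**What the plan says.** Protocol Section 6.3 describes PCPC and POPC as six-point categorical scales that "include death in the scaling (range normal =1 to death =6"). The baseline PCPC is rated from the record and a caregiver interview "within 24 hours of admission for baseline score"; Section 6.1 makes clear that it stands for function before the arrest. PCPC is rated again at 12 months. Section 6.3 then names one PCPC contrast: "The change in PCPC score from 12 months minus baseline (delta PCPC) will be evaluated". It does not say how a death enters that difference, so the value 6 applies.

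Section 4.2 limits the baseline by score at one level only: "Pre-existing severe neurodevelopmental deficits with PCPC =5 or progressive degenerative encephalopathy". Baselines 1, 2, 3 and 4 can therefore enrol.

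The two other outcomes that include death give every death the same worst value. For PRCA, Section 6.3 says "Deaths will be assigned the worst score, 21". For the VABS-3 Mortality Composite Score, Section 9.1 says "Deaths are assigned a score of 0".

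PCPC is the measure named in secondary objective i (Section 1.2).

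**The concern.** A scale that includes death is normally built so that no surviving child ranks below a child who died. PCPC at 12 months has that property, because death is 6 and the worst survival state is 5. Subtracting the baseline removes it. The value of a death then depends on how disabled the child was before the arrest: the more disabled, the smaller the recorded loss. Children with different baselines are no longer ordered by outcome.

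The protocol fixes no analysis for delta PCPC and calls the scale categorical, so ranking or grouping the deltas is a natural choice. In such an analysis some deaths would sit among, or ahead of, severely impaired survivors. A reader who sees a shift in delta PCPC across durations could not tell from the score which of the two had occurred.

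**Working it through.** The protocol states no power, sample size or effect size for delta PCPC, so there is no figure to reproduce. The check is an enumeration.

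**Inputs**
- 12-month PCPC: 1 to 6, death = 6 (Section 6.3).
- Baseline PCPC that can enrol: 1 to 4 (Section 4.2).
- Delta = 12-month PCPC − baseline PCPC; higher is worse (Section 6.3).

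**Step 1: all possible deltas**

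| Baseline | 12-month 1 | 2 | 3 | 4 | 5 | Death (6) |
|---|---|---|---|---|---|---|
| 1 | 0 | +1 | +2 | +3 | +4 | **+5** |
| 2 | −1 | 0 | +1 | +2 | +3 | **+4** |
| 3 | −2 | −1 | 0 | +1 | +2 | **+3** |
| 4 | −3 | −2 | −1 | 0 | +1 | **+2** |

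**Step 2: compare each death with each survivor**

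Death scores strictly better in four pairings:
- death from baseline 3 (+3) against survival at PCPC 5 from baseline 1 (+4)
- death from baseline 4 (+2) against survival at PCPC 5 from baseline 1 (+4)
- death from baseline 4 (+2) against survival at PCPC 4 from baseline 1 (+3)
- death from baseline 4 (+2) against survival at PCPC 5 from baseline 2 (+3)

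Death ties with survival in six pairings:
- baseline 2 death with PCPC 5 from baseline 1 (+4)
- baseline 3 death with PCPC 4 from baseline 1 or PCPC 5 from baseline 2 (+3)
- baseline 4 death with PCPC 3 from baseline 1, PCPC 4 from baseline 2 or PCPC 5 from baseline 3 (+2)

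Strict reversals thus need a death from baseline 3 or 4. A death from baseline 2 can only tie.

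**Step 3: same baseline**

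For any baseline b, death minus survival at PCPC 5 is (6 − b) − (5 − b) = 1. Within a baseline there is no reversal.

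**Step 4: difference in means between arms**

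Mean delta = mean 12-month PCPC − mean baseline PCPC. Baseline precedes randomisation, so in concurrently randomised arms its expected difference is zero. The expected difference in mean delta then equals that in mean 12-month PCPC, where every death is 6. In a linear model that includes baseline PCPC, the estimated duration effect is identical for the two outcomes.

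**Step 5: how many deaths could be involved**

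The protocol gives no baseline PCPC distribution. Its nearest information is in Section 6.1, on the earlier paediatric trial: ">90% had broadly normal function", measured by VABS-2 and not by PCPC. I assume 1–10% with baseline 3 or 4. Survival is 45–55% in most scenarios of Table 9.7.A, so 45–55% die; I assume the same mortality at every baseline.

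Number = 900 × share who die × share with baseline 3 or 4:
- low: 900 × 0.45 × 0.01 = 4.05
- high: 900 × 0.55 × 0.10 = 49.5

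The listed scenarios reach 60% survival (larger effect) and 36% (harmful). These widen the range to 900 × 0.40 × 0.01 = 3.6 and 900 × 0.64 × 0.10 = 57.6.

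**Step 6: after the fix**

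The largest survivor delta is 5 − 1 = +4. With every death at +5, or with the 12-month PCPC itself and death = 6, all four reversals and all six ties disappear.

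**The case against.** **Randomisation balances baseline, and any change score behaves this way.** This largely stands. A reader might infer that the score biases the comparison of durations. The documents do not support that: Step 4 shows the expected difference in means is that of the 12-month PCPC. Section 6.1 also plans to use PCPC to check that baseline function is similar across groups. What it leaves open is the ordering, which matters once deltas are ranked or grouped without adjustment.

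**An arm with more deaths would not look better.** A reader might infer that an arm in which previously disabled children die could look better than one in which those same children survive badly impaired. That is wrong. At a given baseline, replacing survival by death always raises delta, by at least one point.

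**The two ratings differ in method.** Baseline is rated from the record and caregiver interview, while at later times "PCPC/POPC will also be scored at 3 and 12 months by the P-ICECAP neuropsychologist", using the VABS-3 interview. A reader might see a second source of spurious duration effects here. It does not hold as an argument against delta. A baseline rating error enters deaths as well as survivors and has the same expectation in each arm. A shift in the 12-month rating would affect the raw 12-month PCPC equally.

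**The contrast with PRCA and VABS-3 is not like for like.** Fair. Neither has a baseline measurement, so neither could be a change score, and PCPC itself also gives death one fixed value. The contrast shows only the principle applied elsewhere.

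**This belongs in the SAP.** Partly fair. The SAP is not shown, Section 9.9 defers details of secondary analyses to it, and objective i names PCPC and not its change. But the protocol itself defines the measure as a subtraction on a scale with death at 6, and states no exception, although the same section does state a death rule for PRCA.

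**Conclusion.** The point holds in a limited form. As defined in Section 6.3, delta PCPC misorders death and survival across children with different baselines: four pairings are reversed and six tied. Any reversal requires a death from baseline 3 or 4. There is no reversal at a given baseline and no expected bias in the mean difference between concurrently randomised arms. The consequence is a score that is hard to interpret and carries avoidable noise in an unadjusted, rank-based or categorical analysis.

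The size is probably small: about 4 to 50 of 900 children, if 1–10% have baseline 3 or 4 and 45–55% die. The first range is an assumption, and VABS-2 findings in an earlier trial are only an indirect guide to it. The count is of deaths that could be misordered; it does not measure any shift in the estimated effect. The primary outcome, PRCA and the 12-month PCPC itself are not affected.

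**What to change.** In Section 6.3 and the SAP, make the 12-month PCPC (1 to 6, death = 6) the PCPC secondary endpoint, analysed as ordinal with baseline PCPC as covariate. This keeps death worst for every child and still accounts for function before the arrest.

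If delta PCPC is kept, state that every death goes in a single worst category, +5, whatever the baseline.

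Either change takes about one sentence in each document. No new data are needed, since baseline and 12-month PCPC are already collected (Section 6.4). The downside is slightly less direct comparability with any earlier reports that used plain subtraction; these could be matched by a descriptive table of the unadjusted delta.

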6.4 Schedule of Assessments

Measures	Domain	Hospital Day One	Hospital Days Two - Discharge	Hospital Discharge	30-days post OHCA	3-months post OHCA	12-months post OHCA
Demographics (10-20 minutes)	Child/Family Factors	X					
VABS-3 Mortality Composite Score (20-60 minutes)	Neurobehavioral Functioning					X	X
All-cause mortality	Survival				X	X	X
PCPC/POPC (5-10 minutes)	Global neurological and overall functioning	X		X*	X*	X	X
PRCA (40-60 minutes)	Neurological Exam Findings						X
PedsQL (20 - 40 minutes)	Quality of Life and Caregiver Burden	X				X	X
Clinical data / adverse events	Medical Information from chart	X	X	X			

*PCPC/POPC assessed at hospital discharge OR 30 days after OHCA, whichever is earlier

7. MANAGEMENT OF ADVERSE EXPERIENCES

Monitoring of safety is critically important, and among the most central responsibilities of the investigator. The definitions of adverse events (AEs) and serious adverse events (SAEs), expectedness, severity classification, and determination of relatedness are detailed in the extensive Safety Monitoring Plan in the Manual of Procedures.

7.1 Adverse Event Recording

All non-serious AEs occurring through 120 hours from setting the temperature control device to the assigned target and all serious adverse events (SAEs) occurring until participation in study has ended are recorded on the AE case report form (CRF) through the WebDCU™. The Site PI or Study Coordinator or designee is responsible for entering any and all AEs and SAEs into the database as soon as he/she becomes aware of the event and updating the information (e.g., date of resolution, action taken) in a timely manner. All non-serious AEs occurring through 120 hours must be recorded on the electronic AE CRF within 5 days from the time it was discovered by the site study personnel. For SAEs, the data entry must take place within 24 hours of discovery of the event. The NCI Common Terminology Criteria for Adverse Events (CTCAE) (see MoP) will be used to define severity of events.

The Site PI is responsible for the monitoring and follow-up of AEs until resolution or establishment of a new baseline and appropriate documentation in the participant research record. In addition to performing protocol-specified follow up, the participating PI must review all previously reported ongoing AEs to evaluate the current status. Upon completion of the study protocol by the participant, premature withdrawal from the study by the participant, or participant's death, all information regarding each AE must be completed, if not done so earlier.

7.2 Serious Adverse Event Recording and Reporting

All Serious Adverse Events (SAEs) occurring during a participant's study participation will be recorded. All SAEs must be entered into the WebDCU™ system within 24 hours of first knowledge of the SAE by the study team. Additionally, all current study data for that particular participant must be entered to allow for timely review by the medical safety monitors (MSMs). Medical safety monitoring will be conducted as detailed in the P-ICECAP manual of procedures (MoP). The Project Manager forwards all SAE to an internal quality reviewer, and then an independent MSM, within WebDCU™.

